5.1.2 Dose Modifications in Children (<16 years of age)

All pediatric patients will be started on the initial dose of 12 mg/m²/day (Appendix H) orally once per day for 28 days, in 28-day cycles. Dose adjustments based on changes in height and weight may be made every two cycles at the time of restaging evaluations when warranted (restaging CT scans will be performed every 2 cycles during the first 18 cycles; after 18 cycles, restaging CT scans will be performed every 3 cycles; after 36 cycles, restaging CT scans will be performed every 4 cycles; after 60 cycles, restaging CT scans will be performed every 6 cycles).

Dose Modification table for children:

INITIAL DOSE (mg/dose/day)	Reduced dose (mg/dose/day)	% Dose decrease from previous dose
30	20 mg/day	33

20	15 mg/day	25
15	15 mg/day daily for 5 days followed by 2 days rest *	29

*Patients who are receiving antihypertensive medication and require a dose reduction should take antihypertensive medication only on the days of cediranib administration.

Antihypertensive medication should be held during the 2 rest days.

5.2 Dose Reduction

5.2.1 *Hematologic toxicities*

Dose will be modified for grade 4 hematologic toxicity (except lymphopenia, anemia) toxicity. AZD2171 should be held if the ANC is $< 500/\mu\text{L}$ or the platelet count is $< 50,000/\mu\text{L}$ during treatment. The study agent will be held until the ANC is $\geq 1000/\mu\text{L}$ and the platelet count is $\geq 75,000/\mu\text{L}$ (unsupported). Patients who experience any hematologic dose-modifying toxicity (DMT) should be treated at the next lower dose level according to Section 5.1 when sufficiently recovered from toxicity, for subsequent cycles.

5.2.2 *Non-Hematologic toxicities*

AZD2171 should be held in patients who experience grade 3 or greater non-hematologic toxicity until the toxicity returns to grade 1 or baseline, with the following exceptions. Doses will not be held for electrolyte abnormalities unless these are not correctable within 48 hours. Exacerbation of tumor pain can occur with administration of study drug; dose interruption/reduction will not be required for grade 3 or 4 tumor pain. Any patient who has a non-hematological dose-modifying toxicity that does not return to baseline within 14 days while holding drug will be removed from the study. Patients who experience non-hematologic toxicity should have appropriate laboratory testing at least weekly until the toxicity has resolved. Patients who experience any non-hematologic dose-modifying toxicity (DMT) should be treated at the next lower dose level according to Section 5.1 when sufficiently recovered from toxicity, for subsequent cycles.

5.2.3 *Hypertension toxicity*

Therapeutic blood pressure monitoring by a health care provider will occur every 2 weeks during the first 2 cycles, and then at the start of each subsequent cycle for the duration of treatment (unless patients have experienced elevated blood pressure requiring drug therapy). [Table 2](#) will be used for the grading of AZD2171-associated hypertension in adults, for immediate and intermediate-term management, and for the determination of AZD2171 dose modification. An algorithm (Appendix J) will be used for the determination of dose modifications in pediatric patients experiencing dose-limiting toxicity (defined below) for the pediatric population (< 16 years old).

Hypertension toxicity in the pediatric population:

Dose-limiting hypertension is defined as:

- A blood pressure > 25 mmHg above the 95th percentile for age, height, and gender (Appendix I) confirmed by repeated measurement is dose-limiting (see Appendix J for management and grading).

- In patients on antihypertensive therapy, a blood pressure ≤ 25 mmHg above the 95th percentile for age, height, and gender (Appendix J) for > 14 days is dose-limiting (see Appendix F and Appendix J for management and grading).
- Grade ≥ 4 (CTCAE v.5) hypertension.

See Appendix E for instructions on collection and recording blood pressure information and Appendix F for suggested antihypertensive medications by class.

Table 2 outlines toxicity levels in adults based upon a level of elevated blood pressure (systolic and/or diastolic) recorded over a 72-hour period, based upon readings above the 95% for age, gender, and height. The schema of grade, intensity of anti-hypertensive therapy, duration of temporary discontinuation of AZD2171, reduction to the next lower dose level, or permanent discontinuation of drug are intended to allow appropriate, graded medical management for quantitatively graded levels of hypertension, only reducing dose (or ultimately discontinuing therapy) when recognized medical management is unable to restore blood pressure to ‘normative’ levels. Attention to **Table 2** is critical in coding and managing this common complication of AZD2171 in the adult patient population.

Table 2: Management of Hypertension in Adults

BP measurements - systolic/diastolic	Interval	Treatment/Dose Modification
Patients not receiving maximal antihypertensive therapy:		
≥ 150 mmHg (systolic) OR ≥ 100 mmHg (diastolic)	2 BP readings at least 1 hour apart	
 • Add new or additional antihypertensive meds or increase dose of existing meds • Maintain dose of AZD2171
> 200 mmHg (systolic) OR > 110 mmHg (diastolic)	2 BP readings during a 1-week period	
 • Hold AZD2171 • Monitor patient closely for hypotension (if on antihypertensive meds) until AZD2171 is restarted. • Resume treatment when BP falls to $< 150/100$
Patients receiving maximal antihypertensive therapy*:		
> 160 mmHg (systolic) OR > 105 mmHg (diastolic)	2 BP readings at least 1 hour apart	
 • Hold AZD2171 • Maintain antihypertensive meds and monitor patient closely for hypotension until AZD2171 is restarted. • Resume treatment at one lower dose level when BP falls to $< 150/100$

* Maximal antihypertensive therapy is defined as four antihypertensive medications given for 2 weeks.

Notes:

- While patients are receiving treatment with AZD2171, the early initiation of antihypertensive treatment for grade 1 or 2 hypertension to minimize more severe or persistent hypertension is not considered a grade 3 adverse event.

- Decisions to hold or decrease the AZD2171 dose during treatment must be based on BP readings taken in the clinic by a medical professional.

Appendix J outlines the toxicity levels in the pediatric population based on elevated blood pressure measurements repeated on the same day to confirm the elevation. As noted for the adult population, the schema of grade, initiation of anti-hypertensive therapy, duration of temporary discontinuation of study drug, and reduction to the next lower dose level or permanent discontinuation of drug are intended to allow for appropriate grading, management, and consistent safety measures in the pediatric patient population.

Management of Hypertension in Children (<16 yo): See Appendix J

An algorithm will be used to manage AZD2171-related hypertension (Appendix J). Hypertension should be managed with appropriate anti-hypertensive agent(s) as clinically indicated (Appendix F). It is strongly recommended that nephrology or cardiology be consulted in the evaluation and management of hypertension.

Notes:

- **Baseline blood pressure** is defined as the blood pressure obtained at the examination used for study enrollment. This baseline BP should be obtained as follows:
 - 1) Obtain 3 serial blood pressures from the same extremity with the patient in the same position that are separated by at least 5 minutes. Avoid using the lower extremity if possible.
 - 2) Average the systolic blood pressure from the 2nd and 3rd measurements.
 - 3) Average the diastolic blood pressure from the 2nd and 3rd measurements.
 - 4) The baseline BP is the average of the systolic over the average of the diastolic measurements.
- **Elevation** in either the systolic or diastolic blood pressure should be considered when following the algorithm (Appendix J).
 - **The upper limit of normal (ULN)** is defined as a BP equal to the 95th percentile for age, height, and gender (Appendix I).
 - CTC criteria (version 4.0) will be used to determine the grade of hypertension for reporting purposes.
 - Elevated BP measurements should be repeated on the same day to confirm the elevation. Patients with elevated BP should have BP measurements performed at least twice weekly until BP is \leq ULN.

5.2.4 Proteinuria toxicity

Evaluation of urine protein should occur weekly for the first cycle, every other week for cycles 2 and 3, and then once every cycle after if not previously abnormal. [Table 3](#) defines the algorithm for patients with a positive urine dipstick.

Table 3: AZD2171 Dose Modifications for Proteinuria Toxicity Occurring after the First Six Weeks of Therapy

Proteinuria Value	Monitoring	Dose Modification
>1+ (dipstick or equivalent routine laboratory analysis)	Perform the following tests: 
 • 24-hour urine collection for total protein and creatinine • microscopic examination of fresh urine 	See below.
Based on results of the 24-hour urine collection:		
< 1g protein (24-hour collection)	Continue dipstick or equivalent routine laboratory analysis	Continue planned dose.
≥ 1g but ≤ 2g protein (24-hour collection)	Perform 24-hour urine collection (total protein, creatinine) prior to day 1 of each subsequent cycle of therapy (q4w) until total protein is <500 mg/24 hours	Decrease one dose level; continue treatment (only after the first six weeks of therapy).
>2g protein (24-hour collection)	Perform 24-hour urine collection (total protein, creatinine) weekly until proteinuria is < 2g	Hold AZD2171. When protein is < 2g/24 hours, resume treatment at one lower dose level (only after the first six weeks of therapy).
	Perform 24-hour urine collection (total protein, creatinine) prior to day 1 of each subsequent cycle of therapy (q4w)	Continue until patient is off study.

5.2.5 Cardiac Toxicity

For patients who develop compromised LVEF

1. Discontinue AZD2171 in patients who develop symptomatic heart failure;
2. Modify the AZD 2171 dose using the table presented in Appendix G in patients who develop compromised symptomatic LVEF. The NCI developed the table in Appendix G using the NSABP-B31 and NCCTG9831 monitoring guidelines for adjuvant trastuzumab in breast cancer. These studies enrolled populations considered most likely to be cured; thus, the investigators used the most stringent and conservative monitoring.

Note: Only 5 occurrences of compromised LVEF have occurred in 510 patients treated worldwide with AZD2171. Only a small portion of these patients are at increased risk based on the definitions provided in this protocol. Given the risk for and incidence of compromised LVEF secondary to AZD2171 treatment, this level of increased vigilance is sufficient.

5.2.6 Reversible Posterior Leukoencephalopathy Syndrome (RPLS) or similar leukoencephalopathy syndrome

RPLS or clinical syndromes related to vasogenic edema of the white matter have been rarely reported in association with AZD2171 therapy (<3%). Clinical presentations are variable and may include altered mental status, seizure and cortical visual deficit. Hypertension is a common risk factor and was present in most (though not all) patients on AZD2171 who developed RPLS. MRI scans are key to diagnosis and typically demonstrate vasogenic edema (hyperintensity in T2 and FLAIR images and hypointensity in T1 images) predominantly in the white matter of the posterior parietal and occipital lobes; less frequently, the anterior distributions and the gray matter may also be involved. RPLS should be in the differential diagnosis in patients presenting with unexplained

mental status changes, visual disturbance, seizure or other CNS findings. RPLS is potentially reversible, but timely correction of the underlying causes, including control of blood pressure and interruption of the offending drug, is important in order to prevent progression to irreversible tissue damage. AZD2171 should be held in patients with symptoms/signs suggestive of RPLS, pending work-up and management, including control of blood pressure. AZD2171 should be discontinued upon diagnosis of RPLS. After consultation with the principal investigator and CTEP, NCI, consideration of restarting the study may be evaluated in light of any clinical benefit.

5.2.7 *Growth Plate Abnormalities (pediatric patients)*

1D measurement through mid growth plate on sagittal view and volumetric measurements via an automated image analysis adapted from the MEDx software program used for volumetric analysis, will be used to measure growth plate changes. Growth plate expansion greater than 2 times the volume from baseline to interval measurement will be considered dose limiting. AZD2171 should be discontinued upon determination of dose limiting growth plate abnormalities.

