5.1 Dose Modifications

Dose will be modified for grade 3 or greater non-hematologic toxicity (except electrolyte abnormalities unless these are not correctable within 48 hours) and/or grade 4 hematologic (except lymphopenia, anemia) toxicity. A maximum of 2 dose reductions will be allowed before the patient is taken off treatment. Patients who require a dose-reduction will not have the dose re-escalated. No more than 2 dose reductions will be allowed.

If administration of AZD2171 is interrupted for any reason, counting of the cycle days continues (i.e., if a patient stops drug on Day 15 and resumes 2 days later, they will be considered on Day 17).

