Appendix G: LVEF Dose Modification Table

Asymptomatic Decrease in LVEF

The decision to continue or hold STUDY DRUG is based on the LVEF as it relates to the institution's lower limit of normal (LLN) **and** change in ejection fraction from screening (LVEF as measured at registration) according to the following table:

Relationship of LVEF to institution's LLN	LVEF Decrease < 10%	LVEF Decrease 10-15%	LVEF Decrease ≥ 16%
Normal	Continue	Continue	Continue and repeat MUGA/ECHO within 1-2 cycles
1-5% below LLN	Continue and repeat MUGA/ECHO within 1-2 cycles	Continue and repeat MUGA/ECHO within 1-2 cycles	HOLD and repeat MUGA/ECHO within 1-2 cycles
≥ 6% below LLN	Continue and repeat MUGA/ECHO within 1-2 cycles	HOLD and repeat MUGA/ECHO within 1-2 cycles	HOLD and repeat MUGA/ECHO within 1-2 cycles

Discontinue STUDY DRUG if:

- Two consecutive HOLD categories occur.
- Three intermittent HOLD categories occur (at the discretion of the investigator, STUDY DRUG may also be permanently discontinued prior to the occurrence of 3 intermittent HOLD categories).

If LVEF is maintained at a "Continue and repeat MUGA/ECHO" or improves from a HOLD to a "Continue and repeat MUGA/ECHO" category, additional MUGA scans/echocardiograms prior to the next scheduled MUGA/ECHO will be at the discretion of the investigator.

Symptomatic Cardiac Events

Discontinue STUDY DRUG if:

- A patient has symptoms of congestive heart failure (CHF) and a diagnosis of CHF is confirmed.
- A patient has a myocardial infarction.

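### Section 5.2.5 item 2 sends symptomatic LVEF decline to the Appendix G table, which is written for asymptomatic decline (minor; a correction to one phrase)

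*Combined protocol and SAP*

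**What the plan says.** Section 5.2.5 gives two instructions for compromised left ventricular ejection fraction (LVEF). Item 1 is "Discontinue AZD2171 in patients who develop symptomatic heart failure". Item 2 is "Modify the AZD 2171 dose using the table presented in Appendix G in patients who develop compromised symptomatic LVEF".

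Appendix G has two parts. The first, headed "Asymptomatic Decrease in LVEF", contains the only table. It opens with "The decision to continue or hold STUDY DRUG is based on the LVEF", and sets the relation of LVEF to the institutional lower limit of normal against the size of the fall since screening. It then gives discontinuation rules, one of which applies when "Two consecutive HOLD categories occur". The second part covers symptomatic cardiac events and uses no table. It stops the drug after a myocardial infarction, or when "A patient has symptoms of congestive heart failure (CHF) and a diagnosis of CHF is confirmed".

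Two general rules also apply. Section 5.1 states "Dose will be modified for grade 3 or greater non-hematologic toxicity", with an exception for electrolyte abnormalities. Section 5.2.2 states "AZD2171 should be held in patients who experience grade 3 or greater non-hematologic toxicity until the toxicity returns to grade 1 or baseline", with listed exceptions. Section 5.4 separately ends therapy for unacceptable toxicity, or when the principal investigator judges that a change in the patient's condition makes further treatment unacceptable.

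On monitoring, Section 4.1 says that ECHO/MUGA will be done in every pediatric patient at baseline and serially afterwards, and refers to Section 10 for detail. In Section 10 the calendar row is marked at pre-study only. Its note i requires the baseline study, and allows later ones every 2 to 4 cycles if clinically indicated.

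**The concern.** Item 2 names the opposite population from the table it cites. This is an operative rule for holding or stopping a drug with known cardiac effects, so it should be right as written.

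Two groups are affected by a literal reading. A patient with a silent fall in LVEF falls under neither item of Section 5.2.5. A patient with symptoms, but in whom heart failure has not been confirmed, is sent to a table built for people without symptoms, and most of its cells keep the drug going.

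Declines below grade 3 have been seen with this drug. Section 2.2.6 reports non-dose-limiting decreases in 5 of 16 children during cycle 1 of the pediatric phase I trial, and a grade 2 decrease in one patient after cycle 2. The general rules in Sections 5.1 and 5.2.2 act only from grade 3.

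The echo inconsistency is related but lesser. The table can act only on a repeat LVEF value, and a silent decline may give no clinical reason to obtain one.

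**Working it through.** There is no stated figure to reproduce and no power or error-rate calculation involved. The check is a comparison of texts and a count of table cells.

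**1. Count the Appendix G cells.** Input: the three-by-three table in Appendix G.

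| LVEF relative to lower limit of normal | Cells that continue | Cells that hold | Cells asking for a repeat scan |
|---|---|---|---|
| Normal | 3 | 0 | 1 |
| 1-5% below | 2 | 1 | 3 |
| 6% or more below | 1 | 2 | 3 |
| Total of 9 | 6 | 3 | 7 |

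Continue: 3 + 2 + 1 = 6. Hold: 0 + 1 + 2 = 3. Repeat scan: 1 + 3 + 3 = 7. The 6 of 9 is a count of cells, not the probability that a patient is told to continue.

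**2. Take each type of patient through the text as written.**

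- *Symptomatic heart failure.* Item 1 discontinues. The symptomatic block of Appendix G also discontinues once the diagnosis is confirmed. The two agree.
- *LVEF fall with symptoms, heart failure not confirmed.* Item 2 sends this patient to the table. The heading over the table excludes the patient, and 6 of its 9 cells say to continue.
- *LVEF fall without symptoms.* Item 1 does not apply, and item 2 read literally does not apply. The right rule exists in Appendix G, but Section 5.2.5 does not direct this patient to it.

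**3. Ask which reading is intended.** With *asymptomatic* in item 2, item 1 corresponds to the symptomatic block of Appendix G and item 2 to the table. Nothing is duplicated and nothing is left over. With *symptomatic*, the table has no patients directed to it who match its heading. The slip is therefore in item 2, not in Appendix G.

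**4. Check what else could act on a silent decline.** Sections 5.1 and 5.2.2 act at grade 3 or greater. Section 5.4 allows discontinuation for unacceptable toxicity or on the principal investigator's judgement, with no grade limit. The documents give no LVEF cut-points for the toxicity grades, so the overlap between the three hold cells and grade 3 cannot be worked out.

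**5. Compare the two echo statements.** Under Section 4.1 every child has serial studies after baseline, with no interval given. Under note i a child with no clinical indication is required to have none after baseline. Both cannot describe the same schedule.

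**The case against.** The best answer is that the slip corrects itself in use. Nobody can apply the table without opening Appendix G, where the heading is correct, the discontinuation rules are complete and symptomatic events are set apart. The lead-in to Section 5.2.5 also speaks of compromised LVEF without limiting it by symptoms. This stands, and it is the main reason the point is minor. It does not make item 2 right as written.

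Three stronger readings are tempting, and the documents do not support them.

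- *That telling staff to modify the dose conflicts with a table that only continues or holds.* It does not. Tables 2 and 3 list holding the drug, and continuing or maintaining the planned dose, under dose modification, and the title of Appendix G calls it a dose modification table. The absence of dose-level changes in its cells is no defect.
- *That below grade 3 only Appendix G can lead to stopping the drug.* Section 5.4 can too, through unacceptable toxicity or the principal investigator's judgement.
- *That the protocol should require pediatric echoes at a fixed interval.* Section 4.1 gives no frequency and defers to Section 10, so a mandatory interval would be a new commitment. The cited phase I declines arose in cycle 1 and after cycle 2, whereas the children still on drug are far beyond that. The documents do not settle which section should give way.

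It is also fair to say that no harm is shown. Section 2.2.6 does not say whether the grade 2 decrease was silent, gives no value that would place it in a hold cell, and reports improvement in two patients without intervention or dose change.

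**Conclusion.** The concern holds as an error of wording in an operative safety rule. Section 5.2.5 item 2 names symptomatic patients where the cited table is for asymptomatic ones. Taken literally, it leaves Section 5.2.5 without a rule for silent decline and sends symptomatic patients without confirmed heart failure to a table with 6 continue cells out of 9.

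Severity is minor. A reader might infer that patients with silent decline have no protection anywhere in the protocol. That goes too far: Appendix G is correctly labelled, and Sections 5.1, 5.2.2 and 5.4 provide partial cover. Section 2.4 reports that accrual is closed and that two pediatric patients and one adult remain on drug, so 2 + 1 = 3 people are affected from here on. The primary response analysis is untouched.

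The disagreement between Section 4.1 and note i is real but secondary.

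The conclusion rests on the current text alone. It assumes that Appendix G reflects the intended rule, which its internal consistency supports. How often the wording would change a decision cannot be estimated from the documents.

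**What to change.** In item 2 of Section 5.2.5, replace *compromised symptomatic LVEF* with *an asymptomatic decrease in LVEF*. Leave the opening verb and Appendix G as they are. The cost is one phrase in the next amendment, with no new visit, test or data item.

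A patient with symptoms then comes under item 1 and the symptomatic block of Appendix G. While a diagnosis of heart failure is being worked up, Sections 5.1, 5.2.2 and 5.4 apply.

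Separately, make Section 4.1 and note i of the Section 10 calendar say the same thing about follow-up ECHO/MUGA in children. Either direction resolves the mismatch. Aligning Section 4.1 with note i is an edit to the text only. Making the follow-up studies mandatory would add procedures, and the sponsor would need to choose and justify the interval.

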5.3 General Concomitant Medication and Supportive Care Guidelines

All patients will be provided with the best available supportive care. At present, the potential of AZD2171 for clinically significant drug interactions involving the CYP isozymes is unknown. However, studies of the agent in rats indicated possible suppression of CYP1A that may be of biological significance. Efforts should be made to switch patients with brain metastases who are taking enzyme-inducing anticonvulsant agents ([Appendix B](#)) to other medications one week prior to starting therapy. The case report form must capture the concurrent use of all other drugs, over-the-counter medications, or alternative therapies.

5.3.1 *Anti-epileptic drugs*

Anti-epileptic drugs may be used, if indicated. Patients requiring a change in anticonvulsants once on therapy should be switched to an anticonvulsant with a similar effect on hepatic enzymes.

5.3.2 *Febrile neutropenia*

Febrile neutropenia should be managed according to the local institutional guidelines. Measures include laboratory testing, blood and urine cultures, and institution of broad spectrum antibiotics.

5.3.3 *Growth Factors*

Routine use of growth factors (i.e., Filgrastim, Sargramostim, Erythropoietin) is not permitted. However, therapeutic use of filgrastim or sargramostim in patients with serious neutropenic conditions, such as sepsis, may be considered at the investigator's discretion.

5.3.4 *Anti-emetics*

If a patient demonstrates the need for antiemetics, their use will be at the treating physician's discretion.

5.3.5 *Anti-diarrheals*

If diarrhea develops and does not have an identifiable cause other than study drug administration, anti-diarrheals such as Lomotil (diphenoxylate HCl 2.5 mg + atropine sulfate 0.025 mg/tablet) dosed according to package insert or loperamide 4 mg po after the first unformed stool with 2 mg po every 2 hours as long as unformed stools continue (4 mg every 4 hours while asleep). No more than 16 mg of loperamide should be taken in during a 24-hour period. This regimen can be repeated for each diarrheal episode. Diarrhea will be considered refractory if it does not resolve within 24 hours \leq to Grade 2 with the above regimen (16 mg, or less if there is resolution of the symptoms, of loperamide in a 24-hour period).

5.3.6 *Abnormal Thyroid Function*

The treatment of chemical hypothyroidism in patients that are asymptomatic continues to be at the discretion of the treating physician. Patients with symptoms consistent with hypothyroidism require replacement therapy. Currently, no standard is available regarding non-symptomatic patients although the endocrine services at the Dana-Farber Cancer Institute and St. Jude recommend treatment for patients with any degree of chemical hypothyroidism as defined by their laboratory profiles even without symptoms given the overall safety of thyroid replacement.

